12.3 ALLERGIC REACTION TO CONTRAST INJECTION

Possible allergic reaction to the contrast injection must be addressed. A physician experienced with contrast reactions will be available during the contrast scan along with a trained nurse to monitor the subject. The patient will be constantly monitored for contrast reactions, such as itchiness, hives, breathing difficulties. Suitable medical supplies will be on-hand to treat the subject in the rare case of an adverse contrast reaction. See “Management of Acute Reactions to Contrast Media in Adults” document (Appendices G, H), which includes Hives/Urticaria, Diffuse Erythema, Bronchospasm, Laryngeal Edema, Hypotension, Hypertensive Crisis, Pulmonary Edema, Seizures/Convulsions, Hypoglycemia, Anxiety/Panic Attack, and Reaction Rebound Prevention. In the rare case of a severe reaction, the infusion will be stopped immediately, the subject will be treated with suitable medical supplies on hand and 911 will be called. The subject will be transported to the Emergency Department at the University of Rochester, Strong Memorial Hospital.

Possible infection, hematoma and contrast extravasation from IV access may also occur after the IV contrast injection. After the CT exam, the subject will be under observation for at least one hour while she is still in the facility. In the rare case of a severe event, the subject will be treated with suitable medical supplies on hand. (Appendix I)

12.4 MACHINE FAILURE

There is a small risk that the scans may be interrupted by machine failure. If the machine fails during the pre-contrast scan and the contrast injection is not started, the subject may choose to continue the study or withdraw from the study. If the subject chooses to continue the study, the pre-contrast scan will be repeated, followed by contrast injection and post-contrast scan.

Clinical Trial Protocol			
Title:	Contrast-Enhanced Cone Beam Breast CT for Diagnostic Breast Imaging		
Internal #:	16-01		
IRB #:	RSRB00061893	NCT #:	NCT03354611
Revision:	3.5	Effective Date:	

The repeat of the pre-contrast scan will cause extra radiation dose up to one full CBBCT scan (4mGy to 16mGy). Thus, the total radiation dose in case of machine failure will be up to 12mGy to 48mGy depending on breast size and density.

If the machine fails after the contrast injection is started, the scan will not be repeated. The acquired images will be postprocessed to see if the images can be recovered or corrected. If the images can be corrected, the subject will still be included in the study. Otherwise, the subject will be excluded from the study.

There may be risks that are not known at this time.

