3 STUDY ENDPOINT

The primary endpoint of this study is:

- Enrollment of up to 100 evaluable diagnostic patients who successfully finish the study including 30 cancer cases confirmed by pathology results

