5.3 NUMBER OF SUBJECTS

Up to one hundred (100) diagnostic patients will be enrolled and consented to participate in the study. These women will be enrolled from screening recall assigned BIRADS 0, patient complaint, and referral for second opinion. The final diagnostic workup outcome of these enrolled patients need to include:

- At least thirty (30) pathology confirmed cancers
- Various numbers of all BIRADS cases

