9 ANALYSIS OF RESULTS

All data will be collected in a spreadsheet.

Contrast-enhanced CBBCT (CE-CBBCT) for breast imaging will be evaluated, tabulated, and analyzed in terms of lesion conspicuity and detail in comparison with the non-contrast CBBCT exam, mammogram, and contrast-enhanced breast MRI. We will evaluate wash in and wash out patterns and degree of enhancement of the lesion as compared to surrounding pattern.

Demographic and clinical characteristics of the study population will be described using mean and standard deviation for quantitative variables such as age, or percentage and percentiles for qualitative variables such gender, race, and cancer staging.

Reported adverse events will be tabulated according to its description, severity, and relationship to the specific imaging or clinical procedures. All patients will be included in the safety analysis.

Paired t-test (for quantitative measurements such as tumor size, time of wash in and wash out) or McNemar's test (for qualitative data such as type of mass, type of calcification) will be used for comparisons between the CE-CBBCT and other modalities.

Accuracy of diagnosis will be evaluated in terms of sensitivity and specificity by comparing the test results from each imaging modality to that of the biopsy (the gold standard). When sufficient data is available, comparisons between CE-CBBCT and the other modalities will then be conducted using McNemar's test.

No imputation will be used for missing data (i.e., only patients who have the specific data available will be included in a particular analysis.) Statistical analysis will be performed using SAS (SAS Institute, Cary, N.C., U.S.A.). All tests will be 2-sided with the confidence level set to 95%.

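### Section 12.4 excludes from the study, without qualification, a contrast-exposed woman whose images cannot be recovered, which conflicts with Section 9's all-patient safety analysis

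*Protocol*

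**What the plan says.** Section 12.4 separates two situations. If the machine fails during the pre-contrast scan and before injection, the woman may continue or withdraw. The second situation is the one at issue: "If the machine fails after the contrast injection is started, the scan will not be repeated". Her images are then post-processed, with two possible outcomes. The first is "If the images can be corrected, the subject will still be included in the study". The second is "Otherwise, the subject will be excluded from the study". The exclusion is from the study as a whole. The sentence names no analysis set and says nothing about safety.

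Section 9 defines the safety analysis: "Reported adverse events will be tabulated according to its description, severity, and relationship to the specific imaging or clinical procedures", followed by "All patients will be included in the safety analysis". For every other analysis it uses available cases, so that "only patients who have the specific data available will be included in a particular analysis".

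The Section 3 endpoint has a narrower set: "Enrollment of up to 100 evaluable diagnostic patients who successfully finish the study". Section 5.3 sets the enrolment ceiling: "Up to one hundred (100) diagnostic patients will be enrolled and consented to participate in the study".

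**The concern.** The rule in 12.4 turns only on whether images are usable, yet it decides whether a woman remains a subject of the study. She has already been exposed to what the safety analysis is meant to describe. She has had a pre-contrast scan, which 12.4 itself puts at 4 to 16 mGy, and at least part of the iodinated contrast. Sections 6.1 and 6.3.1 give a lower ceiling of about 13 mGy per scan; nothing here depends on which applies.

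This matters because of what the data are for. Section 14 says contrast use with this device is not FDA-approved, and Section 1.2 says a separate submission must show that the contrast exam is safe and effective. The women who received contrast are the natural safety denominator. Section 12.3 also notes that infection, hematoma and extravasation may follow the injection. If site staff took exclusion to mean that data collection ends, no later analysis could recover what was not collected.

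**Working it through.** The plan states no figure on this point, so the main check compares the texts. The arithmetic afterwards is for scale only.

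**Who is affected.** Three conditions must all hold: the machine fails, the injection has already started, and the images cannot be corrected. A woman whose images can be corrected stays in. Under Section 6.2.5 the post-contrast scan starts 90 to 200 seconds after the injection begins, so she may have had all, part or none of the second scan. In every case she has had the first scan and some contrast.

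**The two rules side by side.**
- Section 12.4: not in the study.
- Section 9: all patients are in the safety analysis.

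Both can be followed only if exclusion from the study means exclusion from something narrower, or if an excluded woman still counts as a patient. The protocol says neither. It does have a term for the narrower set, since Section 3 speaks of evaluable patients, but 12.4 does not use it. Section 9 does not say whether its patients are those enrolled, scanned or injected. The revision history suggests how this arose: machine failure entered Section 12 in revision 3.2, and no entry from 3.2 onward lists Section 9.

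**Scale.** Inputs: n = 100 (Section 5.3 ceiling) and f, the proportion of exams that fail after injection starts and cannot be recovered. The protocol gives no value for f, so 1%, 2% and 5% are assumed.

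- Expected number affected = 100 × f.
- Chance of at least one = 1 − (1 − f)^100.
- One-sided 95% upper bound when no events are seen in m women = 1 − 0.05^(1/m). With all 100 women kept, this is 1 − 0.05^(1/100) = 2.95%.

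| Assumed f | Expected affected | Chance of at least one | Safety denominator if excluded | Zero-event upper bound if excluded |
|---|---|---|---|---|
| 1% | 1 | 1 − 0.99^100 = 63% | 99 | 2.98% |
| 2% | 2 | 1 − 0.98^100 = 87% | 98 | 3.01% |
| 5% | 5 | 1 − 0.95^100 = 99% | 95 | 3.10% |

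Dropping one to five women therefore hardly changes precision. The count can change completely: with one woman excluded, a single event in that woman would read 1/100 if she is kept and 0/99 if she is not.

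**The case against.** The strongest reply is that 12.4 is a rule about image usability and was never meant to touch safety. It sits in the risk section, its test is whether images can be corrected, and it fits the evaluable set in Section 3. Section 9 is the only text that defines the safety population, and it makes no exception. On this reading each rule governs its own ground. The reading is reasonable and may well be the intended one, but the protocol does not state it, and the unqualified wording of 12.4 leaves the opposite reading open.

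The second reply is that her experience would be recorded anyway. This stands. Section 12.3 provides monitoring and at least an hour of observation, neither conditional on usable images. Section 13 has contrast administration and scan timing entered on CRF 3. Section 18 requires any reported adverse event to reach the coordinator within 24 hours. The doubt is therefore about the safety table and later follow-up, not about whether an acute reaction would be noticed.

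A reader might also infer that the rule hides device failures or inflates a technical success rate. The documents do not support that. The protocol defines no success rate. Its endpoint counts evaluable finishers, so losing a failed exam makes the target harder to reach. Available-case analysis is stated openly in Section 9. Nothing forbids reporting failures, and a table of them is commonly left to a statistical analysis plan, which is not at hand.

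**Conclusion.** Sections 12.4 and 9 conflict as written over a woman whose scan fails after injection has started and whose images cannot be recovered. The supported conclusion is that a literal reading of 12.4 could take an exposed woman, and any event she has, out of the safety table. It would go too far to say that the protocol definitely removes her.

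The number of women is unknown. The range of 1 to 5 per 100 rests wholly on assumed rates for unrecoverable failures after injection, which are only a subset of all machine failures, and the true rate may be lower. The effect on precision is negligible at any of these rates. The case for a change rests on the contradiction about exposed subjects and the small effort needed to remove it. An unseen analysis plan would not fully settle it, because 12.4 is a rule on who remains in the study and could limit what is collected.

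**What to change.** Reconcile the passages by replacing the last sentence of the post-contrast rule in Section 12.4 with:

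> Otherwise, her images are excluded from the evaluable image dataset; she remains in the study for safety follow-up and in the safety analysis, and the failed exam is recorded and reported as a technical failure among all women scanned.

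Section 9 can then stand as it is. The change leaves the dose, the scan schedule and the rule on repeating a scan as they are. It costs one sentence, and its only downside is that a small number of failed exams will appear in the report.

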13 DATA SAFETY AND MONITORING PLAN

It is prudent to assure that doses remain within the stated limits while continuously monitoring for image quality. We will manage this with the following plan, which will be overseen by the principal investigators:

- The CE-CBBCT system will be calibrated and documented, and periodic quality control testing will be completed and documented to ensure the machine is giving the correct doses of radiation.
- Calculations for target mA and the actual x-ray techniques used will be documented on updated "Technologist Evaluation Form (CRF 3)." This will be used in the annual report to the Radiation Safety Committee which will compare the dose actually used with the radiation estimates provided in the Human Use of Radiation Committee application.
- The ordering and administration of the contrast material and timing of injection and scans will be documented in CRF 3 "Technologist Evaluation Form."
- The exclusion criteria will filter out subjects that have had prior high radiation dose exposure.
- The following will be completed by the Principal Investigator:
 - A periodic review of the Calibration and QC records
 - Review of the mA determination and other technical factors actually used for each subject.
 - Periodically review a sampling of the inclusion/exclusion forms.
- Possible allergic reaction can occur but is rare when using IV contrast agents. A physician and trained nurse experienced with IV contrast reactions will be available during the contrast scan to monitor the subject. Suitable medical supplies will be on hand to treat the subject in the rare case of an adverse contrast reaction.

14 POTENTIAL BENEFITS

The subject may or may not benefit from this study. Although CBBCT device has been approved by the FDA, the use of contrast agent in CBBCT scan has not received FDA approval. If unusual/unexpected findings are noted only in CE-CBBCT, the patient will be referred for further

Clinical Trial Protocol			
Title:	Contrast-Enhanced Cone Beam Breast CT for Diagnostic Breast Imaging		
Internal #:	16-01		
IRB #:	RSRB00061893	NCT #:	NCT03354611
Revision:	3.5	Effective Date:	

workups. It is possible, though not probable, that the patient may have important breast problems identified because of the additional imaging she undergoes with CE-CBBCT.

15 ALTERNATIVES TO PARTICIPATION

The subject may choose not to participate in this trial. Patient care will proceed as normal for each recruiting site. If the patient chooses not to participate in this trial, it will in no way jeopardize current or future care within UR Medicine.

16 RECRUITMENT METHODS

Recruitment of volunteers will be accomplished by each participating site by face-to-face recruitment by the site research coordinator, or radiologist investigators. Site personnel may use appointment schedules to identify patients who may qualify for this study. Every effort will be made to recruit volunteers of ethnic minorities.

Any member of the approved study team will ask the patient if she is interested in hearing about the clinical trial. If the patient is interested, she will be treated as a prospective subject. If the patient meets all the inclusion criteria, none of the exclusion criteria and wishes to continue participating in the study, she will be enrolled into the study. Following this, one of the licensed physicians (MD) or physician assistant (PA) involved in this study will approve and order the contrast-enhanced CBBCT radiographic exam, per NY State laws.

17 CONSENT PROCESS

The study coordinator or any other member of the approved study team, with training through the RSRB Human Subjects Protection Program (or equivalent), will conduct the consent process. The goals of the consent process are to provide information through the IRB-approved study-specific consent form (SSCF) in a non-coercive environment and to engage in an exchange of information about the study in order to assure that the potential participant understands the information so that participation in the study will be voluntary. The consent process will be conducted in a quiet and private area. The prospective subject will be informed that she may take as much time as needed to read the SSCF and that she may also take the consent form home to discuss with family members. Once the potential volunteer has read the consent form, the person obtaining consent will engage in an exchange of information about the study and respond to all questions. If the potential participant indicates that she would like to participate, the person obtaining consent will ask if all her questions have been answered and if she has any other questions. If the prospective subject indicates all questions have been answered and she has nothing further to ask, she will proceed to the consent process: the prospective subject is asked to sign and date the two copies of the consent form. The person obtaining consent will also sign and date both consent forms in the presence of the participant. The subject will then be given one copy of the signed consent form for

Clinical Trial Protocol			
Title:	Contrast-Enhanced Cone Beam Breast CT for Diagnostic Breast Imaging		
Internal #:	16-01		
IRB #:	RSRB00061893	NCT #:	NCT03354611
Revision:	3.5	Effective Date:	

her records, and will be told to call at any time with further questions or concerns about participation in the study.

18 ADVERSE EVENTS

Personnel within UR Medicine will inform the study coordinator of any reported adverse events within 24 hours of knowledge. The study coordinator will immediately report serious adverse events (including serious injury or death) to the IRB and the Sponsor.

19 COMPENSATION FOR INJURY

UR Medicine will provide medical care for any emergency medical problem that the subject may experience as a direct result of participation in this research. The subject will not have to pay for this emergency care, but the University may seek reimbursement for this care from the health insurance carrier or the study sponsor. Decisions regarding care and compensation for any other research related injury will be made on a case-by-case basis.

20 SPONSORSHIP

The study is funded by Koning Corporation, West Henrietta, NY.

21 COST TO THE SUBJECT

There will be no cost to the participant for the CE-CBBCT study.

The subject or her insurance carrier will be charged for focused work-ups based on new findings of the CE-CBBCT, if those occur.

Biopsy and other testing prompted by follow-up standard imaging will be charged to the subject or her insurer.

